## **1.0 AMENDMENT HISTORY**

Amendment No.	Protocol Version No.	Date issued	Author(s) of changes	Details of Changes made

## 2.0 SYNOPSIS

Study Title	The assessment of left ventricular (LV) function in septic shock; comparison of ejection fraction measurement (both by two-dimensional and three- dimensional echocardiography), Global Longitudinal Strain, high sensitivity Troponin and NT proBNP. The assessment of left ventricular function in septic shock; comparison of ejection fraction measurement (both by two-dimensional and three-dimensional echocardiography), Global Longitudinal Strain, high sensitivity Troponin and Pro NT BNP
Short Title	GLASSheart
Internal ref. no.	PHT/2017/431
Problem statement	2D Ejection Fraction (EF) is not universally accurate in identifying LV systolic dysfunction in septic shock. The early identification of systolic dysfunction can assist clinicians in guiding medical therapy to optimise cardiac output and organ perfusion. Other methods of LV assessment such as cardiac magnetic resonance imaging (MRI) or Positron emission tomography (PET) are not routinely performed on this population due to cost, time and practical limitations. The use of 3D EF is currently not routinely recommended by British Society of Echocardiography (BSE) guidelines. This study aims to determine which type of echocardiographic modality identifies the most patients with cardiac dysfunction. In addition, we would like to assess the feasibility of non-invasive cardiac output measurement in the critically unwell patient. Biomarkers commonly used to assess non-septic cardiomyopathies (i.e. NT-proBNP and high sensitivity troponins) will be measured to identify their potential relationship with septic cardiomyopathies. Additionally, individuals who have persistent impaired Global Longitudinal Strain (GLS) are at risk of long-term myocardial dysfunction despite apparent clinical recovery. The study aims to

	identify individuals who would benefit from further cardiology follow up.			
Research question / hypothesis	
 
To identify a possible association between echo assessment with GLS, 2D EF and 3D EF and biomarkers which are conventionally used in myocardial dysfunction.
 
To identify if sequential echocardiographic scans assessing GLS, 2D EF and 3D EF are suitable to monitor progression of cardiac dysfunction following an episode of critical illness.
 
Is GLS a suitable early predictor of cardiac dysfunction (as currently defined by reduced EF) both in the short and longer term in comparison to traditional EF measurements.
 
			
Study Design	A single site, prospective, cohort study.			
Study Participants	
 
In-patients at Queen Alexandra Hospital, Portsmouth with Sepsis and septic shock, specifically:
 
1. Age 18 - 85yrs inclusive
 
2. Sepsis and septic shock as defined by Sepsis-3 criteria
 
3. Admitted to the Intensive Care Unit (ICU)
 
			
Planned Sample Size	108			
Follow-up duration	1yr			
Planned Study Period	3 years			
Primary Objective	• Can 3D LVEF, or GLS, provide an earlier indicator of LV failure in sepsis and septic shock compared to 2D LVEF?			
Secondary Objectives	
 
To explore any practical barriers to using GLS and three- dimensional echo methods by cardiac physiologists
 
Is three-dimensional EF feasible in the ICU population?
 
To investigate whether there is an association between major adverse cardiac events at 12 months post sepsis or septic shock and any abnormal echocardiography results at any time point
 
			

	
 
To investigate whether there is an association between major adverse cardiac events at 12 months post sepsis or septic shock and any abnormal biomarker results at any time point
 
To compare 2D and 3D echocardiographic measurements with GLS to determine whether currently used definition of abnormality in GLS is appropriate.
 
To compare 2D and 3D echocardiography measurements with GLS to identify if a range of abnormal GLS could be mapped to ranges of abnormal echocardiography results
 
To compare troponin and BNP results with GLS to identify if a range of abnormal
 

	biomarker results
Endpoints	• GLS at 24h, 72h, 30 days and 90 days
	• 2D EF and 3D EF at 24h, 72h, 30 days and 90 days
	• NT-proBNP at 24h, 72h, 30 days and 90 days
	High sensitivity troponin at 24h, 72h, 30 days and 90 days
	ICU mortality
	In hospital mortality
	• 30 or 90 day mortality
	
 
hospital re-admission of any cause
 

	Major adverse cardiovascular events (MACE) at 12 months
Eligibility Criteria	Inclusion criteria:
	1. Age 18-85yrs inclusive
	2. Sepsis or septic shock as defined by Third International Consensus Definition for Sepsis and Septic Shock (Sepsis-3)
	3. Admission to ICU
	
 
Informed consent taken after discussion with participant or with consultee if appropriate and a period of reflection of up to 18hours. All participants or consultees will be given Patient information sheet (PIS). Please refer to section 10.1 and 10.2
 

lin.

discussing the issues concerning consent in an unconscious study participant.
Exclusion <del>criteria :criteria:</del>
1. Pregnancy or complications thereof
2. ESRF requiring dialysis or CKD with eGFR<30ml/min
3. Cardiac transplant recipient

 
Uncorrected valvular dysfunction (graded as moderate or severe)
 

5. Known structural heart disease

 
Pre-existing cardiomyopathy with bundle branch block on electrocardiogram (ECG)
 

7. Previous cardiac valve replacement
8. Post-operative within last 7 days

 
Atrial fibrillation/flutter or frequent ventricular ectopic beats during image acquisition
 

10. Death likely within 24 hours in the opinion of the assessing clinician

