#### The aims

There are various novel ways to assess the pumping function of the heart. This can be done with 2D and 3D assessment. A further technique is GLS which measures the change of muscle size and movement at different parts of the heart muscle. The aim of this study is to assess which of these techniques is best to identify patients with LV dysfunction. The relationship of each of these tests with the patients blood test will also be assessed.

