## **Preliminary Studies**

Previous audit and service evaluation have been performed in 2017 for submission as abstracts to Intensive Care Society (ICS) and British Society of Echocardiography (BSE) looking at feasibility of performing the novel echo techniques and to identify a subset of patients who may show normal EF but reduced GLS while in septic shock [1,2,3,4,5]. It showed a discrete group of septic patients in whom there was normal 2D LVEF, but a decrease in GLS. It also showed that although the number of scans able to permit retrospective GLS calculation was low, that this is due to an easily remedied factor at our control. The image optimisation to enable GLS calculation is subtly different than the requirements of standard 2D EF. Without knowing that GLS was to be performed, the staff had not acquired images compatible for GLS. Staff training has already been carried out to correct this and the majority of equipment on site now supports 3D and GLS.

The lead investigator is an experienced echocardiographer with accreditation by the BSE and has undertaken courses on 3D and GLS. Co-investigators are experienced clinical staff

with in depth knowledge of the intensive care patient and a focus in cardiology and/or echo. The cardiology and critical care departments are well resourced to support the study throughout its course.

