## 6.0 AIMS AND OBJECTIVES

### 6.1 **Primary Objective**

Can 3D LVEF, or GLS, provide an earlier indicator of LV failure in sepsis and septic shock compared to 2D LVEF?

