#### 6.2 Secondary Objectives

- To explore any practical barriers to using GLS and three-dimensional echo methods by cardiac physiologists
- Is three dimensional EF feasible in the ICU population?
- To investigate whether there is an association between major adverse cardiac events at 12 months post sepsis or septic shock and any abnormal echocardiography results at any time point
- To investigate whether there is an association between major adverse cardiac events at 12 months post sepsis or septic shock and any abnormal biomarker results at any time point
- To compare 2D and 3D echocardiographic measurements with GLS to determine whether currently used definition of abnormality in GLS is appropriate.
- To compare 2D and 3D echocardiography measurements with GLS to identify if a range of abnormal GLS could be mapped to ranges of abnormal echocardiography results
- To compare troponin and BNP results with GLS to identify if a range of abnormal GLS could be mapped to ranges of abnormal biomarker results
- Can troponin or pro NT BNP measurements in combination with 3D LVEF, 2D LVEF or GLS provide an earlier indicator of LV failure in sepsis or septic shock

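### The primary question has no criterion for LV failure apart from the readings being compared, and neither a count of abnormal results nor the planned ANOVA of means can show earlier detection

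*Protocol*

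**What the plan says.** The Protocol states its purpose in several ways.

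- Synopsis, Problem statement: "This study aims to determine which type of echocardiographic modality identifies the most patients with cardiac dysfunction". The same box says of the comparator: "2D Ejection Fraction (EF) is not universally accurate in identifying LV systolic dysfunction in septic shock". It names cardiac MRI and PET as other methods but notes that they "are not routinely performed on this population due to cost, time and practical limitations".
- Synopsis, Research question: "Is GLS a suitable early predictor of cardiac dysfunction (as currently defined by reduced EF) both in the short and longer term", with traditional EF measurement as the comparison.
- Lay Summary, The aims: "The aim of this study is to assess which of these techniques is best to identify patients with LV dysfunction".
- Section 6.1, repeated in substance in Section 7.2 as the primary outcome measure: "Can 3D LVEF, or GLS, provide an earlier indicator of LV failure in sepsis and septic shock compared to 2D LVEF". Neither section defines LV failure.
- Section 6.2, fifth objective: "To compare 2D and 3D echocardiographic measurements with GLS to determine whether currently used definition of abnormality in GLS is appropriate".
- Section 5.0, Preliminary Studies, describes a group of septic patients in whom "there was normal 2D LVEF, but a decrease in GLS".

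The primary analysis in Section 14.1 is a one-way repeated measures ANOVA. Scans are planned at 24 h, 72 h, 30 days and 90 days. The Synopsis also lists mortality and 12-month MACE as endpoints, and Section 6.2 relates MACE to any abnormal echo result at any time.

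**The concern.** To call one modality an earlier indicator than another, the plan must say what it indicates and how a reader would know that the early signal was right. The Protocol gives no such criterion separate from the scan readings under comparison. The Synopsis offers a count, the research question offers reduced EF, and the primary objective offers an undefined term.

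The count and the EF definition pull in opposite directions for the patients who motivated the study, those with normal 2D LVEF and low GLS. On a count they are extra cases found. Against EF at the same scan they are discordant. Only follow-up can tell whether they are early disease or over-calls, and the stated primary analysis does not follow them as a group. The trial could therefore end with a clear difference between modalities and still not answer its primary question.

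**Working it through.** The Protocol gives no figure for this point, so there is none to reproduce. The check has four parts.

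**1. What each stated approach can show**

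| Approach | Where | What it yields | Shows a true, earlier sign? |
|---|---|---|---|
| Number of patients identified | Synopsis, Problem statement | Count of abnormal results per modality | No: true and false positives are added together |
| Reduced EF as the definition, GLS as early predictor | Synopsis, Research question | A longitudinal question | Could do so, but no analysis is attached |
| Earlier indicator of LV failure | Sections 6.1, 7.2 | The primary question | Not until LV failure is defined |
| One-way repeated measures ANOVA | Section 14.1 | Differences between mean values | No: a mean difference does not say who becomes abnormal first, or whether the abnormality was real |
| Abnormal echo at any time against MACE | Section 6.2 | Association with an external outcome | Partly: it does not isolate normal EF with low GLS |

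**2. Why a count does not separate detection from over-calling (illustration only)**

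Inputs: N = 108 (Section 9.0) and prevalence 14% (the upper figure in Section 4.0). Sensitivity (Se) and specificity (Sp) are assumptions.

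Flagged = N × [prev × Se + (1 − prev) × (1 − Sp)]; PPV = N × prev × Se ÷ flagged.

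| Test | True positives | False positives | Flagged | PPV |
|---|---|---|---|---|
| Perfect | 15.1 | 0 | 15.1 | 1.00 |
| Se 0.80, Sp 0.95 | 12.1 | 4.6 | 16.7 | 0.72 |
| Se 0.85, Sp 0.70 | 12.9 | 27.9 | 40.7 | 0.32 |
| Uninformative, flags half | 7.6 | 46.4 | 54.0 | 0.14 |

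By count the uninformative test ranks first. With an assumed prevalence of 30% it still does (54.0, against 50.2 for Se 0.85/Sp 0.70, 32.4 for the perfect test and 29.7 for Se 0.80/Sp 0.95). At 50%, the Se 0.85/Sp 0.70 test ranks first (62.1), ahead of the perfect test (54.0). The perfect test does not rank first alone at any of the three.

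This shows only how a count behaves. Section 4.0 says that LVEF is typically used to define the condition, so calling everyone outside the 14% a false positive takes EF as the truth. The table is not evidence about GLS in this cohort.

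**3. What 12-month MACE could add for the discordant group**

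Assumptions: 89 patients (the uninflated figure in Section 9.0), the discordant group is 20% to 40% of them, 10% MACE in the rest, two-sided 5% normal-approximation test of two proportions, 80% power. The detectable MACE rate in the group is 39.5% at a 20% share (17.8 patients), 36% at 30% (26.7) and 34.5% at 40% (35.6). With only 45 patients left it is 53.5%, 49% and 47%. MACE can inform on the group, but only large differences would show.

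**4. Precision of a predictive analysis**

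If 14% applies and cases are defined by EF, the cohort holds about 108 × 0.14 = 15.1 cases, including those already reduced at 24 h. Conversions from normal would be fewer. Even with 15 conversions, 12 of them preceded by an abnormal reading (an assumed sensitivity of 80%), the 95% Wilson interval runs from 0.55 to 0.93.

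**The case against.** The strongest reply is that the count wording stands only in the Synopsis problem statement. The operative objective and outcome ask about earliness, and the ANOVA counts no one. That stands. A reader might infer that the modality flagging most patients will be declared best, but this needs the Synopsis sentence joined to the Lay Summary, which does not say that best means most flagged. The Synopsis sentence also refers to patients with dysfunction, not to every positive result.

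Three other strong readings fail as well.

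- A reader might infer that 2D EF is right by definition and every low GLS with normal EF is wrong. The research question is longitudinal: it asks about early prediction in the short and longer term, and Section 4.0 gives the hypothesis that GLS falls before EF. Discordance at one scan is the state being followed.
- A reader might infer that the fifth secondary objective will shift the GLS cut-off to agree with EF. It says only that the measures will be compared. It does not say that the comparison is at the same scan, or that EF will overrule GLS.
- A reader might infer that the discordant group cannot be judged. Serial scans, biomarkers, mortality and 12-month MACE are all collected.

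It may also be said that accuracy measures belong in an SAP, which is not at hand. Their detail may. The target condition of the primary question is the Protocol's to define, and the primary method is already fixed there as a comparison of means. Finally, later 2D LVEF is itself an imperfect reference. That is true, and is why outcome data are needed as support.

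**Conclusion.** The concern holds in this form: the Protocol fixes no criterion for LV failure separate from the index readings being compared, and neither the count in its Synopsis nor the ANOVA in Section 14.1 can answer the primary question. This rests on the text alone and on no assumed sensitivity, specificity or prevalence. The flag-count table is illustrative and says nothing about how GLS or 3D EF will perform here. In particular, it gives no basis for stating how many patients would be falsely flagged or reclassified.

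The Protocol collects what is needed to inform on the discordant group, but no stated analysis isolates that group. On the assumptions shown, MACE alone would be weak evidence: detectable rates are about 35% to 40% against 10% with 89 patients, and 47% to 54% with 45. The point is a worthwhile correction at low cost. It does not show that the study rewards over-calling or is unable to judge GLS.

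**What to change.** 1. Replace the count wording in the Synopsis with the primary objective, and bring the Lay Summary into line.
2. State as the primary analysis: among patients with normal 2D LVEF at the 24 h scan, test abnormal GLS and abnormal 3D EF at 24 h, at cut-offs fixed in advance, as predictors of reduced 2D LVEF at 72 h, day 30 or day 90. Report sensitivity, specificity and predictive values with intervals, and say how deaths before the later scans are accounted for.
3. Report low GLS with normal EF at the same scan as discordance. Relate that group to 12-month MACE and mortality as supporting evidence, because later 2D LVEF is an imperfect reference.
4. In the fifth secondary objective, add later LVEF and 12-month outcome to the comparison with EF. Do not use a cut-off derived in this cohort for the primary question.

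**Cost.** Rewording and some extra analysis, with no new measurement. The Synopsis, the Lay Summary table and the Section 10.0 schedule all include 2D echo at 72 h. Appendix 1, in the copy at hand, shows no tick there and should be checked. The main downside is statistical: few patients will convert from normal to reduced LVEF, so intervals will be wide, and the Protocol should say so.

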## **3.0 ABBREVIATIONS**

BP	Blood Pressure
NT -proBNP	N terminal pro-B-Type Natriuretic Peptide
BSE	British Society of Echocardiography
CKD	Chronic Kidney Disease
СО	Cardiac Output
DCCQ	Department of Critical Care
ECG	Electrocardiogram
ECHO	Echocardiogram
EF	Ejection Fraction
e-GRF	Estimated Glomerular Filtration Rate
ESRF	End Stage Renal Function
GLS	Global Longitudinal Strain
GFR	Glomerular Filtration Rate
HR	Heart Rate
HF	Heart Failure
ICU	Intensive Care Unit
ICS	Intensive Care Society
LV	Left ventricle
LVEF	Left Ventricular Ejection Fraction
MACE	Major adverse cardiovascular events
NCEPOD	National Confidential Enquiry into Patient Outcome and Death
NHS	National Health Service
NRES	National Research Ethics Service
PiCCO	Pulse index Contour Continuous Cardiac Output
PEEP	Positive End-expiratory Pressure
PRA	patient research ambassadors

PPE	Personal protective equipment
SAE	Serious Adverse Event
SOP	Standard Operating Procedure
TTE	Transthoracic Echocardiogram/Echocardiography
UoP	University of Portsmouth
QAH	Queen Alexandra Hospital
2D	Two dimensional
3D	Three dimensional

#### 3.0 LAY SUMMARY

#### Assessing Heart Function in Septic Shock (the GLASSheart study)

#### Background

Sepsis is a life-threatening condition that is triggered by infection. In sepsis, the body's defence mechanism is highly active which results in inflammation. Each year in the United Kingdom (UK), about 200,000 people develop sepsis. Previous research indicates that early recognition and treatment with antibiotics are the most important factors for patient survival. Septic shock is an advanced form of sepsis.

Ultrasound of the heart (Transthoracic Echocardiography (TTE) is used to identify the effect of sepsis on the heart. This is called septic cardiomyopathy, which means a poorly functioning heart muscle due to an infection in the blood. In septic cardiomyopathy the main pumping chamber of the heart, the left ventricle (LV), begins to fail (dysfunction). This in turn will ultimately affect the blood supply of other organs. The current method for assessing the function of the heart with ultrasound is to measure the percentage of blood pump out of the heart with each beat ('ejection fraction' (EF). The way it is measured means it is not accurate for example in critically ill patients with sepsis or septic shock.

#### The aims

There are various novel ways to assess the pumping function of the heart. This can be done with 2D and 3D assessment. A further technique is GLS which measures the change of muscle size and movement at different parts of the heart muscle. The aim of this study is to assess which of these techniques is best to identify patients with LV dysfunction. The relationship of each of these tests with the patients blood test will also be assessed.

#### Methodology

Each patient will have four scans and three blood tests as part of the study alongside standard care, see table below.

1 st scan (24hrs on meeting criteria	2 nd scan (72hrs later)	3rd scan (30days +/-5 days after 1st )4th scan (90days +/- 5days after 1st)		
2d echo	2d echo	2d echo	2d echo	
3d echo	3d echo	3d echo	3d echo	
GLS echo	GLS echo	GLS echo	GLS echo	
BNP blood test		BNP blood test	BNP blood test	
High sensitivity troponin blood test		High sensitivity troponin blood test	High sensitivity troponin blood test	
Table 1) Schedule of data collection.				

### 4.0 BACKGROUND AND RATIONALE

#### Epidemiology

Sepsis-induced cardiomyopathy occurs in up to 14% of patients with sepsis, resulting in myocardial dysfunction [1]. Transthoracic echocardiographic (TTE) assessment of left ventricular ejection fraction (LVEF) is typically used to define sepsis-induced cardiomyopathy. Recent meta-analysis demonstrates that low LVEF was not associated with mortality in septic patients [2,3].

Critically ill patients with sepsis were statistically significantly more likely to have low Global Longitudinal Strain (GLS) compared with reduced LVEF [4,5]. However these studies have been conducted with a small sample size. In addition, there has been no previous exploration of the value of biomarkers and the correlation with LV function.

#### Benefits of Research

The aim of the study is to aid identification of septic cardiomyopathy with GLS earlier than with standard methods. This will enable to initiate treatment early and subsequently impact on patient outcome. TTE at 30 and 90 days in patient who have clinically recovered from septic shock will guide the need for cardiology follow up to detect signs of LV dysfunction early.

This study aims to identify these patients earlier and subsequently aims to improve quality of life, symptom relief and ultimately prevent the need for implantable devices to assist the heart in functioning appropriately.

Prompt and early identification of cardiomyopathy of sepsis facilitates targeted management and may prevent the global organ dysfunction associated with septic shock. Current methods for assessing cardiac function within critical care are limited to either 2D echocardiogram or invasive monitoring such as pulmonary artery catheters and pulse index contour cardiac output monitoring (PiCCO) or other similar devices. They all have relative advantages and disadvantages. Invasive methods can be associated with vascular complications. The use of the pulmonary artery (PA) catheter is not recommended in current practice.[6]. The use of 2D echo for estimation of EF is variable from point of image acquisition to visual interpretation. It is thought that reduced EF seen in 2D and 3D echocardiography is preceded by reduced GLS[1,2,4].

